#### **6.1.2. Study Day**

Day 1 is defined as the date of first dose of randomized treatment. Study day is calculated relative to the date of Day 1.

#### **6.1.3. Adjustments for Covariates and Subgroup Analyses**

##### **6.1.3.1. Covariates**

Disease history (newly diagnosed or relapsing) will be taken into account by including as a stratification variable or covariate in all of the analyses except for the Chi-Square analyses. Due to the small number of PF subjects expected to be enrolled in the study, the randomization strata of disease type will not be included as a covariate in any of the analyses.

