### Double blind randomized trial

- CS taper in all arms to 5 mg/day from end of consolidation period
- Primary analysis adjusted for stratification factors (PV vs PF, and relapsing vs newly diagnosed disease)

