#### **Primary:**

The proportion of patients who are in CR from Week 29 (Visit) to Week 37 (Visit) with a CS dose of  $\leq 10$  mg/day.

- A Cochran-Mantel-Haenszel (CMH) general association test stratified by disease type (PV or PF) and disease history (newly diagnosed or relapsing) will be used to compare rilzabrutinib with placebo. Newly diagnosed pemphigus is defined as patients diagnosed  $\leq 6$  months prior to Screening. Relapsing, chronic pemphigus is defined as patients diagnosed  $> 6$  months prior to Screening.

Patients who drop out of the trial, withdraw, or who receive a rituximab dose prior to Week 37 will count as non-responders in the analysis.

The primary efficacy analysis will be performed using a CMH general association test stratified by disease history (newly diagnosed or relapsing) to compare rilzabrutinib with placebo.

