### 3.5. Method of Assigning Subjects to Treatment Groups

Patients who meet study criteria will be randomly assigned to placebo or PRN1008 in an approximately 1:1 allocation ratio. The randomization scheduled will be computer generated using a permuted block algorithm stratified by PV/PF disease type and by relapsing/newly diagnosed disease history (newly diagnosed defined as within 6 months of Screening).

The randomization schedule will be prepared by Premier Research before the start of the study. No one involved in the study performance will have access to the randomization schedule before the official unblinding of treatment assignment. No subject will be randomized into this study more than once.

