##### **6.1.4. Multiple Comparisons**

The type I error rate of  $\alpha = 0.05$  will be maintained for the study by using sequential (hierarchical) testing for the primary and key secondary endpoints.

The testing will be done in the following order:

1. Primary endpoint based on PV patients in mITT population

2. Primary endpoint in mITT population (ie, PV+PF patients)
3. Key secondary endpoints based on PV patients in mITT population (in the order presented in Section 2.3.2.2)
4. Key secondary endpoints in mITT population (ie, PV+PF patients) (in the order presented in Section 2.3.2.2)

The study will be declared to be a positive study if the p-value for the primary endpoint based on PV patients in the mITT population is significant at two-sided  $\alpha = 0.05$  level. The test stops as soon as an endpoint is found not statistically significant at  $\alpha=0.05$  (2-sided). The nominal p-values for subsequent tests without adjustment will be provided in the summary tables for information purpose.

All other endpoints will be considered exploratory, and no adjustments will be made for multiple comparisons.

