To ensure the overall type I error rate of  $\alpha = 0.05$  will be maintained for the study, hierarchical testing, based on a fixed sequence procedure, will be used for the primary endpoint and continuing for the key secondary endpoints. The CMH primary analysis, as described in Section 8.1, will be the starting point for the hierarchical testing. If statistical significance is declared for the primary analysis, formal hypothesis testing will continue for the key secondary endpoints in sequence (see Section 6.1.3 for sequence of testing) until a non-significant result is reached. All other p-values from secondary and exploratory endpoints, after a non-significant p-value is reached, will be considered nominal. All statistical tests will be performed using two-tailed tests.

For Cochran-Mantel-Haensel tests, if stratum cell sizes are too small based on the Mantel-Fleiss criterion (Mantel, 1980) a Pearson Chi-square test will be used instead without stratification for disease history. If expected cell counts for the unstratified test are less than 5, a Fisher's Exact test will be used.

Analysis of covariance model residuals for the key secondary endpoint evaluated graphically for normality (e.g. quantile-quantile plot) and variance homogeneity (residual plots); additionally, a Kolmogorov-Smirnov test will be performed. A non-parametric will be considered appropriate if the two-sided p-value for the test is significant at the 0.01 level. If a parametric analysis is indicated, a rank analysis of covariance (Stokes, Davis, and Koch, 2000) will be used.

All analyses will be performed on the mITT Population as described in Section 5. Due to the small number of PF subjects expected to be enrolled in the study, the randomization strata of disease type (PV, PF) will not be included as a covariate in any of the analyses.

The analyses for efficacy endpoints involving clinical assessment CR in the blinded treatment period will be performed based on data collected on on-site visits (i.e., not including data collected from remote visits) as the primary analyses. Supportive analysis will be performed by using data collected from all visits including visits performed remotely.

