## 8.1. Primary Efficacy Analysis

The primary efficacy endpoint is the proportion of patients who are in CR from Week 29 to Week 37 with a prednisone dose of  $\leq 10$  mg/day in patients treated with PRN1008 compared with placebo.

Allow  $p_0$  to represent the proportion of responders in the placebo group;  $p_1$  will represent the proportion of responders in the PRN1008 group. The null and alternative hypotheses are:

$$H_0: p_1 - p_0 = 0$$

The proportion of patients who are in CR from Week 29 to Week 37 with a prednisone dose of  $\leq 10$  mg/day does not differ between the two treatment groups.

$$H_1: p_1 - p_0 \neq 0$$

The proportion of patients who are in CR from Week 29 to Week 37 with a prednisone dose of  $\leq 10$  mg/day differs between the two treatment groups.

The primary endpoint will be analyzed using a CMH test, stratified by disease history. The observed number and proportion of subjects meeting the primary endpoint as well as the proportion difference (PRN1008 – placebo), estimated standard error (SE), 95% CI and the associated p-value will be reported.

Descriptive summaries of patients who are in CR with a CS dose of  $\leq 10$  mg/day will also be provided by visit through Week 37.

*These analyses will be performed on the mITT Population as well as in study subgroups as described in Section 6.1.3.2.* As a sensitivity analysis to the primary endpoint, disease type will be included as an additional stratification factor in the CMH test.

Tipping point analyses (Yan, 2009) will be done to investigate the impact of missing data and lost to follow-up (LTF). The tipping point analysis will look at all possible combination of converting missing data to a responder, starting at 0 and ending at all are responders. The cases where the statistical significance tips from significance to non-significance (defined as a two sided p-value  $> 0.05$ ) will be listed. A complete list of all combinations will also be presented. If the imbalances that leads to a change in interpretation are clinically implausible then the results of the primary analysis will be deemed reliable.

In addition, the following endpoints will be analyzed as supportive analyses to primary endpoint:

- Time to first CDA from Baseline to Week 37
- Time to CR from Baseline to Week 37

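### The PV+PF primary test leaves out disease type, a randomisation stratum, and the documents disagree about this

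*SAP*

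**What the plan says.** **Randomisation.** SAP 3.5 allocates patients "using a permuted block algorithm stratified by PV/PF disease type and by relapsing/newly diagnosed disease history". The protocol synopsis (Randomization) names the same two factors.

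**SAP, primary test.** Table 6 and Section 8.1 stratify the CMH test by disease history only. Section 6.1.3.1 gives the reason, the small number of PF patients expected, and says that "the randomization strata of disease type will not be included as a covariate in any of the analyses". Section 8 repeats this. Section 8.1 then plans a sensitivity analysis in which "disease type will be included as an additional stratification factor in the CMH test".

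**SAP, hierarchy (6.1.4).** Step 1 is the primary endpoint in PV patients, and it alone decides whether the study is positive. Step 2 is "Primary endpoint in mITT population (ie, PV+PF patients"). Every key secondary endpoint comes after step 2.

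**Protocol.** The schema in Section 1.2 states "Primary analysis adjusted for stratification factors (PV vs PF, and relapsing vs newly diagnosed disease"). Section 9.3.5 first says "A Cochran-Mantel-Haenszel (CMH) general association test stratified by disease type (PV or PF) and disease history (newly diagnosed or relapsing) will be used". The same subsection ends with "The primary efficacy analysis will be performed using a CMH general association test stratified by disease history (newly diagnosed or relapsing").

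**Precedence.** The protocol synopsis (Other Statistical Considerations) lets the SAP prevail on statistical matters. SAP Section 10 records no change from the planned analysis.

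**The concern.** The usual rule is to analyse by the factors used to stratify the randomisation. Stratified blocks make the arms nearly equal in their PV/PF mix. If PV and PF patients respond at different rates, that balance makes the true variance of the treatment difference smaller than the variance estimated by a test that ignores disease type. The test then runs below its nominal 5% and gives up power.

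The loss falls on step 2. That step must pass before any key secondary endpoint can be tested, including those restricted to PV patients.

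The stated reason does not support the choice. A CMH test pools differences across strata and does not need each stratum to be large. The SAP also already has a rule for sparse tables, which applies "if stratum cell sizes are too small based on the Mantel-Fleiss criterion".

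Separately, a pivotal trial should not reach unblinding with two specifications of its primary test in the protocol.

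**Working it through.** **1. The plan's own power figure.** The current sample-size sections show no numbers. The amendment history (Protocol Version 5, 12.13.9) gives 50% versus 15%, at least 55 per arm (45 PV), a two-sided 0.05 chi-square test and power above 90%, for the earlier endpoint. With

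z = [0.35√n − 1.96√(2 × 0.325 × 0.675)] / √(0.50 × 0.50 + 0.15 × 0.85),

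n = 45 gives z = (2.348 − 1.298)/0.614 = 1.71, power 95.6%. n = 55 gives z = 2.11, power 98.3%. The figure is reproduced.

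**2. Type I error when disease type is ignored.** Inputs: about 120 patients with at most 22 PF (Protocol 4.1), taken as 98 PV + 22 PF, weights 0.8167 and 0.1833. The response rates are assumptions.

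- Within-type variance: W = 0.8167·p_PV(1 − p_PV) + 0.1833·p_PF(1 − p_PF)
- Pooled variance: V = p̄(1 − p̄)
- R = W/V, and actual size = 2[1 − Φ(1.96/√R)]

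Example, PV 15%, PF 50% in both arms: W = 0.1041 + 0.0458 = 0.1500. p̄ = 0.2142, so V = 0.1683. R = 0.891, 1.96/√R = 2.076, and the size is 3.8%.

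| Null rates PV / PF | Formula, history only | Simulated, history only | Simulated, both factors |
|---|---|---|---|
| 15% / 15% | 5.0% | 4.9% | 4.9% |
| 15% / 30% | 4.7% | 4.7% | 5.0% |
| 15% / 40% | 4.3% | 4.3% | 4.9% |
| 15% / 50% | 3.8% | 3.7% | 4.9% |
| 20% / 45% | 4.4% | 4.3% | 4.9% |
| 20% / 70% | 3.0% | 3.0% | 5.0% |

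Each simulated figure uses 200,000 trials. The 15% PV rows use permuted blocks of 4; block sizes 2 and 6 gave similar results. The 20% PV rows use exactly balanced strata.

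**3. Power.** Per arm: PV 20 newly diagnosed + 29 relapsing, PF 4 + 7 (40% newly diagnosed, assumed), no effect of history. For stratum h with N_h patients, m_h responders, n_1h and n_0h patients per arm and a_h responders on active, the statistic is

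[Σ(a_h − n_1h·m_h/N_h)]² / Σ[n_1h·n_0h·m_h(N_h − m_h) / (N_h²(N_h − 1))],

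rejecting above 3.84, with 200,000 trials per row. Figures are percentages, history only → four strata.

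| PV placebo/active | PF placebo/active | Step 2 | Steps 1 and 2 together |
|---|---|---|---|
| 20/42 | 20/42 | 74.7 → 74.9 | 63.4 → 63.4 |
| 15/35 | 30/50 | 69.5 → 70.4 | 59.1 → 59.5 |
| 20/42 | 45/67 | 71.7 → 73.6 | 61.7 → 62.5 |
| 15/35 | 50/75 | 70.5 → 74.8 | 59.7 → 61.3 |
| 15/35 | 60/80 | 65.2 → 71.8 | 57.4 → 60.4 |
| 15/50 | 15/50 | 98.9 → 99.0 | 96.8 → 96.8 |
| 15/50 | 50/85 | 98.6 → 98.9 | 96.7 → 96.8 |
| 15/50 | 60/80 | 96.8 → 97.5 | 95.7 → 96.2 |

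With permuted blocks of 4 (block size assumed) and random stratum sizes, 60,000 trials, the losses for PF 45/67, 50/75 and 60/80 were 1.4, 3.8 and 6.0 points at step 2, and 0.6, 1.5 and 2.9 points for both steps.

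**4. Would four strata be too sparse?** With balanced arms and low rates, the Mantel-Fleiss sum is about half of all responders however the strata are cut. At a 15% rate that is 120 × 0.15 / 2 = 9, above the limit of 5. The fallback was triggered in 0.0% of trials in every power scenario above and in at most 1.0% of the no-effect trials. If both arms responded at 10% the sum would be about 6 and the fallback would fire in about 23% of trials, but the same arithmetic applies to the history-only test.

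**The case against.** **The conflict is mostly editorial.** The SAP is uniform about the primary test itself; only its phrase covering all analyses clashes with a sensitivity analysis labelled as such. The SAP prevails over the protocol, so the operative test is known. The amendment history (12.13.1) also shows that the last sentence of Protocol 9.3.5 entered as the PV-only analysis, where history alone is the right stratification, and later lost that label. All of this stands. It narrows the SAP inconsistency to a wording slip, but the protocol text still needs repair.

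**The larger losses need large PV–PF gaps.** Nothing in the documents suggests that PF placebo response is 25 to 45 points above PV. With gaps of 10 to 15 points the step-2 loss was 0.2 to 0.9 points, depending on how allocation was simulated. This stands, and the figures have to be read as a range.

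**22 PF patients is a ceiling.** For PV 15/35 and PF 50/75, the step-2 loss falls to 2.3 points with 12 PF patients and 1.5 with 8; the both-steps loss falls to 1.2 and 1.0. This also stands.

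**Fewer strata is a defensible choice in a small trial.** This does not hold here. Four strata did no worse, beyond simulation error of about 0.1 point, in any scenario, including smaller PF counts and PF responding less than PV.

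**Conclusion.** The point holds, with limited stakes. The step-2 test omits a randomisation factor for a reason that does not justify it. It is conservative whenever PV and PF rates differ: mildly for gaps up to about 25 points (size 4.2% to 4.7%), and down to about 3% for gaps of 45 to 50 points.

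The figure that matters most is the chance of passing steps 1 and 2 together, because step 2 counts only after step 1. Four strata add 1 to 3 points there in the less favourable scenarios and at most about half a point elsewhere.

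The PV-only test is unaffected and no error rate is inflated. These sizes rest on assumed PF rates, 22 PF patients, 40% newly diagnosed and no effect of disease history. The direction does not depend on those values, and no scenario favoured the history-only test beyond simulation error.

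**What to change.** Settle this before unblinding.

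- **SAP 6.1.3.1, 8, 8.1 and Table 6:** stratify the PV+PF primary CMH test by disease type × disease history, and make the history-only version the sensitivity analysis. Keep history only for the PV test. Keep the Mantel-Fleiss fallback. Reword the statement that bars disease type from every analysis.
- **SAP 6.1.3.1, step 4:** say explicitly whether disease type enters the PV+PF key secondary models. The simulations here do not cover those models, but the same sentence governs them.
- **Protocol 9.3.5:** attach the two-factor sentence to the PV+PF population and the history-only sentence to the PV population. The schema in Section 1.2 then agrees for PV+PF.

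The cost is one stratum variable and some wording, plus the usual handling of an SAP revision and a protocol text correction. Both tests are already planned, and no patient, visit or data item changes.

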##### **6.1.3.2. Subgroup Analyses**

Subgroup analyses of the primary endpoint will be conducted by

- race (White, Non-White),
- age group (< 40, 40-64, >64),
- gender (male, female)
- disease history (newly diagnosed, relapsing),
- disease diagnosis category (PV, PF)
- disease severity (moderate [PDAI 9-45], severe [PDAI ≥ 46])

Key secondary endpoints will also be analyzed by the above subgroups.

##### **6.1.4. Multiple Comparisons**

The type I error rate of  $\alpha = 0.05$  will be maintained for the study by using sequential (hierarchical) testing for the primary and key secondary endpoints.

The testing will be done in the following order:

1. Primary endpoint based on PV patients in mITT population

2. Primary endpoint in mITT population (ie, PV+PF patients)
3. Key secondary endpoints based on PV patients in mITT population (in the order presented in Section 2.3.2.2)
4. Key secondary endpoints in mITT population (ie, PV+PF patients) (in the order presented in Section 2.3.2.2)

The study will be declared to be a positive study if the p-value for the primary endpoint based on PV patients in the mITT population is significant at two-sided  $\alpha = 0.05$  level. The test stops as soon as an endpoint is found not statistically significant at  $\alpha=0.05$  (2-sided). The nominal p-values for subsequent tests without adjustment will be provided in the summary tables for information purpose.

All other endpoints will be considered exploratory, and no adjustments will be made for multiple comparisons.

### 6.1.5. Handling of Dropouts or Missing Data

All possible efforts will be made to ensure that subjects stay in the study and all data is collected as scheduled. Any subject who withdraws from the study or misses a scheduled visit will have their primary and secondary efficacy analyses missing data imputed prior to analysis according to criteria described in this section. Safety data (with the exception of AE and concomitant medication date/times as described in Section 6.1.10) will not be imputed and will be analyzed as observed.

#### 6.1.5.1. Imputation Procedures for the Primary Efficacy Endpoint

For the primary efficacy endpoint (the proportion of patients who are in CR from Week 29 to Week 37 with a prednisone dose of  $\leq 10$  mg/day), patients with missing data due to study withdrawal will be considered as non-responders. A patient who received a rituximab dose prior to Week 37 will also be counted as a non-responder. [REDACTED]

[REDACTED]

- [REDACTED]
- [REDACTED]

[REDACTED]

[REDACTED]

[REDACTED]

[figure not shown]
[REDACTED]

[REDACTED]

Tipping point analyses (Yan, 2009) will be done to investigate the impact of missing data and lost to follow-up (LTF). The tipping point analysis will look at all possible combination of

converting missing data to a responder, starting at 0 and ending at all are responders. The cases where the statistical significance tips from significance to non-significance (defined as a two sided p-value  $>0.05$ ) will be listed. A complete list of all combinations will also be presented. If the imbalances that leads to a change in interpretation are clinically implausible then the results of the primary analysis will be deemed reliable

#### **6.1.5.2. Imputation Procedures for Secondary Endpoints**

### Responder analyses:

If a patient received a rituximab dose prior to Week 37, the patient will be counted as a non-responder starting from the date of first dose of rituximab for following responder analyses:

- The proportion of patients who are in CR from Week 29 to Week 37 with a CS dose of  $\leq 5$  mg/day
- The proportion of patients who have a PDAI score  $< 3$  from Week 29 to Week 37 with a CS dose  $\leq 10$  mg/day

For the derivation of the following parameters:

- proportion of patients having three or more lesions within 1 month or extension of established lesions that do not heal within 1 week from Baseline to Week 37
- proportion of patients with at least one disease flare/relapse from initial control of disease activity (CDA) to Week 37,

A missing value will be considered as Yes with exception of the following:

- A 'No' can be inferred if adjacent visits are complete and reflect this same outcome. No more than one disease assessment can be imputed for this endpoint (i.e. this imputation is not applicable to consecutive missing visits). Note that, this imputation is not applicable at Week 37 when the study treatment a patient receives before and after the visit could be different.

If a patient received a rituximab dose prior to Week 37, the patient will be counted as Yes for the analyses of these two parameters.

### Time to event analyses:

For the analyses of following parameters,

- Time to first CR with a CS dose  $\leq 10$  mg/day CS, from Baseline to Week 37
- Time to first CR with a CS dose  $\leq 10$ mg/day, from Baseline to Week 61
- Time to initial flare/relapse from initial CDA to Week 37.

If a patient receives a rituximab therapy, the study data will be censored at the date of first rituximab administration for the above time to event analyses.

